1.4 STUDY PLAN

[figure not shown]
This is a multicenter, 56-week, randomized, double-blind, placebo-controlled Phase 3 study consisting of 4 study periods:

- A 2-week Screening Period (11 to 14 days)

- A 30-week double-blind, placebo-controlled Core Treatment Period, for efficacy and safety assessment
- A 26-week double-blind, placebo-controlled Treatment Extension Period; participants will remain on the randomized investigational medicinal product (IMP) regimen
- A 6-week Follow-up Period to collect posttreatment safety information for all participants after last dose of IMP

The maximum study duration per participant will be 64 weeks with treatment lasting for 56 weeks (a 30-week core treatment period and a 26-week extension period). The graphical study design is shown in [Figure 1](#).

Figure 1 - Study Design Overview

The end of the study is defined as the date of the last visit of the last participant in the study.

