2.1.4 Safety endpoints

The safety analysis will be based on the reported adverse events (AE), hypoglycemia and other safety information, such as clinical laboratory data, vital signs, and ECG.

Observation period

The observation period related to treatment will be divided into 3 main segments:

- The **pre-treatment** period is defined as the time from informed consent up to the time of first injection of IMP
- The whole **on-treatment** period is defined as the time from the first injection of the IMP up to 30 days (7 days for hypoglycemia) after the last injection of the IMP
 - The 30-week core on-treatment period is defined as the time from the first injection of IMP up to Visit 9 (Week 30) (or Day 210 if Visit 9 [Week 30] visit is missing) or up to 30 days (7 days for hypoglycemia) after the last injection of IMP, whichever comes earlier
- The **post-treatment** period is defined as the period from the end of the whole on-treatment period.

The **on-study observation period** is defined as the time from first injection of IMP up to either the last protocol-planned visit or the date of last available information if participants discontinue the study prematurely (ie, the date collected on e-CRF page “Completion of End of Study/Follow-up”), whichever is later.

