2.4.4.2 Analysis of Hypoglycemia

Treatment-emergent hypoglycemia events will be tabulated separately from the AEs.

Event frequency and incidence of hypoglycemia events will be summarized by treatment for all reported hypoglycemia and per type of hypoglycemic event described in [Section 2.1.4.5](#) (ie, severe, documented symptomatic, asymptomatic, probable symptomatic, relative). Documented hypoglycemia (symptomatic or asymptomatic) will be also evaluated for the more stringent plasma glucose threshold of <3.0 mmol/L (<54 mg/dL), as well as for ≥ 3.0 and <3.9 mmol/L (≥ 54 and <70 mg/dL), and <3.9 mmol/L (<70 mg/dL). Frequency and percentage of participants with at least 1 hypoglycemia event will be summarized as well.

Event rate of hypoglycemia per participant year will be calculated by treatment using the total number of hypoglycemia events from all participants (denoted as n) divided by the total exposures from all participants expressed in years (ie, participant exposure in days divided by 365.25, denoted as t). Multiple events from an individual participant will all count. Event rates of hypoglycemia per participant year [all reported hypoglycemia, severe, documented symptomatic, asymptomatic, probable symptomatic, relative hypoglycemia, and documented hypoglycemia with plasma glucose <3.0 mmol/L (<54 mg/dL) as well as for ≥ 3.0 and <3.9 mmol/L (≥ 54 and <70 mg/dL), and <3.9 mmol/L (<70 mg/dL)] will be presented by treatment group for the whole on-treatment period.

A listing of participants for all severe hypoglycemia events reported on the specific eCRF “Hypoglycemic Event Information” page will be provided.

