2.5.3 Missing data

For categorical variables, participants with missing data are not included in calculations of percentages unless otherwise specified. When relevant, the number of participants with missing data is presented.

Derived variables will be considered missing if any of the original variables required to calculate them are missing. For example, if either a baseline assessment or an endpoint assessment is missing for a particular participant, then change from baseline at endpoint will be missing. Depending upon the assessment, analyses may not include all participants in the analysis population, because certain participants in the intended population may have missing data.

Handling of computation of treatment duration if investigational medicinal product end of treatment date is missing

For the calculation of the treatment duration, the date of the last dose of IMP is equal to the date of last administration reported on the treatment status case report form page. If this date is missing, the exposure duration should be left as missing.

In the definition of the whole on-treatment period, the date of the last dose of IMP is equal to the date of the last administration reported on the treatment status case report form page. If this date is missing, the date of the last IMP injection in the exposure page will be used for participants with at least 1 injection or the date of visit 2/randomization visit will be used for participants who were lost to follow-up after the initial dispensation of IMP.

Handling of medication missing/partial dates

No imputation of medication start/end dates or times will be performed. If a medication date or time is missing or partially missing and it cannot be determined whether it was taken prior or concomitantly, it will be considered a prior, concomitant, and posttreatment medication.

Handling of adverse events/hypoglycemia with missing or partial date/time of onset

Missing or partial AE/hypoglycemia onset dates and times will be imputed so that if the partial AE/hypoglycemia onset date/time information does not indicate that the AE/hypoglycemia started prior to treatment or after the whole on-treatment period, the AE/hypoglycemia will be classified as treatment-emergent. No imputation of AE end dates/times will be performed. These data imputations are for categorization purpose only and will not be used in listings. No imputation is planned for date/time of AE resolution.

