Handling of adverse events/hypoglycemia when date and time of first investigational medicinal product administration is missing

When the date and time of the first IMP administration is missing, all AEs/hypoglycemia that occurred on or after the day of randomization should be considered as TEAEs. The exposure duration should be kept as missing.

Handling of potentially clinically significant abnormalities

If baseline is missing, the participant will be grouped in the category “normal/missing at Baseline.”

For PCSAs with 2 conditions, one based on a change from Baseline value or a normal range and the other on a threshold value, with the first condition being missing, the PCSA will be based only on the second condition.

Handling of missing screening value to derive randomization strata

In case of missing data at screening visit for HbA1c, unscheduled data before randomization visit can be used. If the sample is confirmed as being for the purpose of a re-screen, then the result is sent to be integrated into IRT. In case of several data collected, the earliest is used.

Participants who do not have a documented stable daily dose of SU for at least 3 months prior to screening will be considered non-SU users.

Linked adverse events that worsened or became serious

An AE that worsened or became serious will have a separate record in the data from the original event record with a reference identification number that links the new record to the original record. An AE that worsened or became serious will be considered a new recurring AE in the summary of recurrent events or in the summary of events by time intervals.

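### When the last-dose date is missing, SAP 2.5.3 still counts a participant's hypoglycemia events but leaves their exposure out, so the rate per participant-year comes out slightly too high.

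*SAP*

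**What the plan says.** SAP 2.4.2.1 computes exposure in days as last dose date minus first dose date plus 7, and refers to 2.5.3 for missing data. SAP 2.1.4 runs the on-treatment period from the first injection "up to 30 days (7 days for hypoglycemia) after the last injection of the IMP". SAP 2.4.4.2 defines the hypoglycemia rate as the "total number of hypoglycemia events from all participants (denoted as n) divided by the total exposures from all participants expressed in years".

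SAP 2.5.3 then has two adjacent rules for a last-dose date missing from the treatment status page:

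- Treatment duration: "If this date is missing, the exposure duration should be left as missing".
- On-treatment period: "the date of the last IMP injection in the exposure page will be used for participants with at least 1 injection". For participants lost to follow-up after the first dispensing, the Visit 2 date is used.

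The same section covers a missing first-dose date: "all AEs/hypoglycemia that occurred on or after the day of randomization should be considered as TEAEs", followed by "The exposure duration should be kept as missing".

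SAP 2.3.2 foresees such participants. Someone who was dispensed IMP and then lost, with no record either way, is treated as exposed and stays in the safety population.

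**The concern.** With both dates present the two parts of the rate match: exposure adds 7 days after the last dose, and the hypoglycemia window closes 7 days after the last injection. The match fails only when a date is missing. The participant then has a defined window, and events that count, but no person-time.

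The number of hypoglycemic events per participant-year is a secondary safety endpoint in Protocol Section 3, Table 1. Whenever there are events and person-time is dropped, the error is upward. The same person-time is also lost from the cumulative exposure reported under SAP 2.4.2.1. The percentage of participants with at least one event is not affected.

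**Working it through.** The documents give no hypoglycemia rate, expected event count or number of missing dates, so there is no planned figure to reproduce. The check applies the SAP's own formula.

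**Inputs**

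- Participants per arm: 100 (SAP 1.1 and 1.3).
- Full exposure: the last weekly dose falls on Day 1 + 7 × 55 = 386, so exposure is 386 − 1 + 7 = 392 days (formula in SAP 2.4.2.1).
- Participant lost straight after dispensing: the fallback last dose is Visit 2, Day 1, so exposure would be 1 − 1 + 7 = 7 days.
- Assumptions: k participants lack the date and would have d days each; the others have L days each. L is 392, or 196 if early termination halves exposure.

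**Formula**

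Let N be all counted events, T all person-time, and Tm the person-time left missing. The SAP's rules give N/(T − Tm). The matched rate is N/T. The relative excess is

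T/(T − Tm) − 1 = Tm/(T − Tm) = k·d / ((100 − k)·L).

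It does not depend on the event rate.

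**Results**

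| k | d (days) | L (days) | Calculation | Excess |
|---|---|---|---|---|
| 1 | 7 | 392 | 7 / 38,808 | 0.02% |
| 10 | 7 | 392 | 70 / 35,280 | 0.2% |
| 1 | 7 | 196 | 7 / 19,404 | 0.04% |
| 10 | 7 | 196 | 70 / 17,640 | 0.4% |
| 1 | 98 (a quarter of full) | 392 | 98 / 38,808 | 0.25% |
| 1 | 392 | 392 | 392 / 38,808 | 1.0% |
| 5 | 392 | 392 | 1,960 / 37,240 | 5.3% |

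At an assumed true rate of 2 per participant-year, ten participants lost after dispensing (L = 392) give 2 × 1.0020 = 2.004. One fully exposed participant gives 2 × 1.0101 = 2.020. The last row needs several long-exposed participants without a date, which nothing in the documents suggests.

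**Alternative reading**

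If affected participants are left out of both parts, the rate is (N − Nm)/(T − Tm), where Nm is their events. This is internally consistent, and equals N/T when their event rate is the same as everyone else's.

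**The case against.** **Exclusion may be intended.** SAP 2.5.3 says in general that "analyses may not include all participants in the analysis population, because certain participants in the intended population may have missing data". A programmer could take this to remove affected participants from both numerator and denominator. But the sentence only permits omission, does not mention event counts, and stands against a rate formula that takes events from all participants. Two programmers could both comply and report different rates.

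**Missing dates should be rare.** Protocol 7.1 requires every IMP discontinuation to be fully documented. For the first dose the case is stronger still: Protocol 6.1, Table 2 has Dose 1 given on site at Visit 2 and the date and time of each injection recorded, and Protocol 6.4 has the monitor check the administration page. This stands. The first-dose rule has the same split, but should almost never be used.

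**A stronger reading that fails.** The first-dose rule restates no end date, and SAP 1.4 plans "A 6-week Follow-up Period to collect posttreatment safety information for all participants after last dose of IMP". A reader might infer that hypoglycemia long after the last dose is counted without limit. The documents do not support that. The rule replaces a missing start. SAP 2.1.4 and 2.1.4.1 still confine treatment-emergent events to the on-treatment period, which for hypoglycemia closes 7 days after the last injection, and SAP 2.4.4.2 presents the rates for that period.

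**It hardly matters.** The trial stopped early, the SAP is a simplified one for a synopsis report (SAP 1.6), and safety is descriptive without systematic testing (SAP 2.4.4). This limits the importance of the point but does not make the two rules agree.

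**The remedy is a choice.** The SAP deliberately leaves exposure missing, and using Visit 2 as the last dose credits 7 days to someone whose dosing is undocumented. That is fair, and it is why exclusion from both parts is also acceptable.

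**Conclusion.** The point holds for a missing last-dose date. As written, the rules count events without their person-time and overstate the rate by Tm/(T − Tm). The likeliest case, loss straight after dispensing, gives about 0.02% to 0.4% for one to ten participants in an arm of 100, the upper figure assuming exposure halved to 196 days. One fully exposed participant adds about 1.0%. The effect is zero if no dates are missing, and the documents give no count. The missing first-dose rule shares the mismatch but should be very rare. This is a minor correction: the analysis is descriptive, and nothing here suggests a materially wrong safety conclusion.

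**What to change.** In SAP 2.5.3:

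1. For the hypoglycemia rate denominator, derive exposure from the same fallback dates that define the on-treatment period: the last injection on the exposure page, or Visit 2 if lost after dispensing. Use the randomization date if the first-dose date is missing.
2. Apply these dates to all the exposure summaries in SAP 2.4.2.1 (cumulative, duration and category) or to none. Using them for cumulative exposure alone would make it disagree with the duration and category tables.
3. Report per arm how many participants needed a fallback date. The n in the duration summary shows this only indirectly. The SAP's provision for presenting numbers with missing data appears in its text on categorical variables and applies only when relevant.

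Alternatively, state that participants with missing exposure are excluded from both numerator and denominator. This is consistent but discards their events.

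The cost is about two sentences and a small derivation change, with no new data. The downside is that a few exposure values would rest on the exposure page or a visit date instead of the treatment status page.

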2.5.4 Windows for time points

Nominal post-baseline visits will be used for descriptive statistics and time course plots.

Efficacy data at Week 30 / Week 56

The scheduled measurements at the endpoint visit (Week 30 or Week 56) as collected will be used in the efficacy analyses including those obtained after IMP discontinuation and/or introduction of rescue therapy. For participants whose efficacy measurement is not available at the endpoint visit, the measurement at unscheduled visit (including the end of treatment and/or study visit for those prematurely discontinued) will be used if the unscheduled measurement is within +/-30 days (7 days for FPG) of the date of the endpoint visit [targeted study Day 210 for Week 30 (or Day 392 for Week 56)]. If multiple measurements are associated to the same targeted date, the closest to the targeted study day will be used. In case of equality, the last measurement will be used. If there are still no measurement for a given parameter at an endpoint visit, the data is considered missing for efficacy analyses.

2.5.5 Unscheduled visits

Unscheduled visit measurements will be used for computation of Baseline and PCSA.

2.5.6 Pooling of centers for statistical analyses

Not applicable.

2.5.7 Statistical technical issues

Not applicable.

3 INTERIM ANALYSIS

No interim analysis is planned.

4 DATABASE LOCK

The database is planned to be locked approximately 4-6 weeks after last participant last visit.

5 SOFTWARE DOCUMENTATION

All summaries and statistical analyses will be generated using SAS version 9.3 or higher.

7 LIST OF APPENDICES

[Appendix A](#) Criteria for Potentially Significant Abnormalities

[Appendix B](#) Schedule of Activities

Appendix A Criteria for Potentially Significant Abnormalities – for Phase 2/3 studies (oncology excepted)

Parameter	PCSA	Comments
Clinical Chemistry		
ALT	By distribution analysis : >3 ULN >5 ULN >10 ULN >20 ULN	Enzymes activities must be expressed in ULN, not in IU/L. Concept paper on DILI – FDA draft Guidance Oct 2007. Internal DILI WG Oct 2008. Categories are cumulative. First row is mandatory. Rows following one mentioning zero can be deleted.
AST	By distribution analysis : >3 ULN >5 ULN >10 ULN >20 ULN	Enzymes activities must be expressed in ULN, not in IU/L. Concept paper on DILI – FDA draft Guidance Oct 2007. Internal DILI WG Oct 2008. Categories are cumulative. First row is mandatory. Rows following one mentioning zero can be deleted.
Alkaline Phosphatase >1.5 ULN		Enzymes activities must be expressed in ULN, not in IU/L. Concept paper on DILI – FDA draft Guidance Oct 2007. Internal DILI WG Oct 2008.
Total Bilirubin	>1.5 ULN >2 ULN	Must be expressed in ULN, not in μ mol/L or mg/L. Categories are cumulative. Concept paper on DILI – FDA draft Guidance Oct 2007. Internal DILI WG Oct 2008.
Conjugated Bilirubin	>35% Total Bilirubin and TBILI>1.5 ULN	Conjugated bilirubin dosed on a case-by-case basis.

Parameter	PCSA	Comments
ALT and Total Bilirubin	ALT>3 ULN and TBILI>2 ULN	Concept paper on DILI – FDA draft Guidance Oct 2007. Internal DILI WG Oct 2008. To be counted within a same treatment phase, whatever the interval between measurements.
CPK	>3 ULN >10 ULN	FDA Feb 2005. Am J Cardiol April 2006. Categories are cumulative. First row is mandatory. Rows following one mentioning zero can be deleted.
CLcr (mL/min)	<15 (end stage renal disease)	FDA draft Guidance 2010
(Estimated creatinine clearance based on the Cokcroft-Gault equation)	≥15 - <30 (severe decrease in GFR) ≥30 - <60 (moderate decrease in GFR) ≥60 - <90 (mild decrease in GFR) ≥90 (normal GFR)	Pharmacokinetics in patients with impaired renal function-study design, data analysis, and impact on dosing and labeling
eGFR (mL/min/1.73m ²)	<15 (end stage renal disease) ≥15 - <30 (severe decrease in GFR) ≥30 - <60 (moderate decrease in GFR) ≥60 - <90 (mild decrease in GFR) ≥90 (normal GFR)	FDA draft Guidance 2010 Pharmacokinetics in patients with impaired renal function-study design, data analysis, and impact on dosing and labeling
Creatinine	≥150 µmol/L (Adults) ≥30% change from baseline ≥100% change from baseline	Benichou C., 1994.

Parameter	PCSA	Comments
Uric Acid		Harrison- Principles of internal Medicine 17 th Ed., 2008.
Hyperuricemia	>408 µmol/L	
Hypouricemia	<120 µmol/L	
Blood Urea Nitrogen	≥17 mmol/L	
Chloride	<80 mmol/L >115 mmol/L	
Sodium	≤129 mmol/L ≥160 mmol/L	
Potassium	<3 mmol/L ≥5.5 mmol/L	FDA Feb 2005.
Total Cholesterol	≥7.74 mmol/L	Threshold for therapeutic intervention.
Triglycerides	≥4.6 mmol/L	Threshold for therapeutic intervention.
Lipasemia	≥3 ULN	
Amylasemia	≥3 ULN	
Glucose		
Hypoglycaemia	≤3.9 mmol/L and <LLN	ADA May 2005.
Hyperglycaemia	≥11.1 mmol/L (unfasted); ≥7 mmol/L (fasted)	ADA Jan 2008.
HbA1c	>8%	
Albumin	≤25 g/L	
CRP	>2 ULN or >10 mg/L (if ULN not provided)	FDA Sept 2005.

Parameter	PCSA	Comments
Hematology		
WBC	<3.0 Giga/L (Non-Black); <2.0 Giga/L (Black) ≥16.0 Giga/L	Increase in WBC: not relevant. To be interpreted only if no differential count available.
Lymphocytes	>4.0 Giga/L	
Neutrophils	<1.5 Giga/L (Non-Black); <1.0 Giga/L (Black)	International Consensus meeting on drug-induced blood cytopenias, 1991. FDA criteria.
Monocytes	>0.7 Giga/L	
Basophils	>0.1 Giga/L	
Eosinophils	>0.5 Giga/L or >ULN (if $ULN \geq 0.5$ Giga/L)	Harrison- Principles of internal Medicine 17 th Ed., 2008.
Hemoglobin	≤115 g/L (Male); ≤95 g/L (Female) ≥185 g/L (Male); ≥165 g/L (Female)	Criteria based upon decrease from baseline are more relevant than based on absolute value. Other categories for decrease from baseline can be used (≥ 30 g/L, ≥ 40 g/L, ≥ 50 g/L).
Decrease from Baseline ≥ 20 g/L		
Hematocrit	≤0.37 v/v (Male) ; ≤0.32 v/v (Female) ≥0.55 v/v (Male) ; ≥0.5 v/v (Female)	
RBC	≥6 Tera/L	Unless specifically required for particular drug development, the analysis is redundant with that of Hb. Otherwise, consider FDA criteria.
Platelets	<100 Giga/L ≥700 Giga/L	International Consensus meeting on drug-induced blood cytopenias, 1991.

Parameter	PCSA	Comments
Urinalysis		
pH	≤4.6	
	≥8	
Vital signs		
HR	≤50 bpm and decrease from baseline ≥20 bpm ≥120 bpm and increase from baseline ≥20 bpm	To be applied for all positions (including missing) except STANDING.
SBP	≤95 mmHg and decrease from baseline ≥20mmHg ≥160 mmHg and increase from baseline ≥20 mmHg	To be applied for all positions (including missing) except STANDING.
DBP	≤45 mmHg and decrease from Baseline ≥10 mmHg ≥110 mmHg and increase from Baseline ≥10 mmHg	To be applied for all positions (including missing) except STANDING.
Orthostatic Hypotension		
Orthostatic SDB	≤-20 mmHg	
Orthostatic DBP	≤-10 mmHg	
Weight	≥5% increase from baseline ≥5% decrease from baseline	FDA Feb 2007.
ECG		
		Ref.: ICH E14 guidance (2005) and E14 Q&A (2012), and Cardiac Safety Research Consortium White Paper on PR and QRS (Nada et al. Am Heart J. 2013; 165(4) : 489-500)
HR	<50 bpm <50 bpm and decrease from baseline ≥20 bpm	Categories are cumulative

Parameter	PCSA	Comments
	<40 bpm <40 bpm and decrease from baseline ≥ 20 bpm <30 bpm <30 bpm and decrease from baseline ≥ 20 bpm	
	>90 bpm >90 bpm and increase from baseline ≥ 20 bpm >100 bpm >100 bpm and increase from baseline ≥ 20 bpm >120 bpm >120 bpm and increase from baseline ≥ 20 bpm	
PR	>200 ms >200 ms and increase from baseline $\geq 25\%$ >220 ms >220 ms and increase from baseline $\geq 25\%$ >240 ms >240 ms and increase from baseline $\geq 25\%$	Categories are cumulative
QRS	>110 ms >110 msec and increase from baseline $\geq 25\%$ >120 ms >120 ms and increase from baseline $\geq 25\%$	Categories are cumulative

Parameter	PCSA	Comments
QT	>500 ms	
QTc	Absolute values (ms)	To be applied to any kind of QT correction formula. Absolute values categories are cumulative
	>450 ms	
	>480 ms	QTc >480 ms and $\Delta QTc > 60$ ms are the 2 PCSA categories to be identified in individual subjects/patients listings.
	>500 ms	
<hr/>		
Increase from baseline		
Increase from baseline]30-60] ms		
Increase from baseline >60 ms		

